6.1.5 Dose Modifications and Discontinuation

There are no planned modifications to dose, other than discontinuation.

The schedule may be modified if a participant has symptoms or signs on the day of scheduled immunisation, and the investigator considers it best to defer the immunisation. The participant will be asked to return for review within the window period of the scheduled immunisations (-3/+7 days from week 4, 8 and 20 for the second, third and fourth immunisations respectively).

A clinical investigator may decide to permanently discontinue dosing in a participant who has received one or more immunisations, if the investigator deems that continuing might compromise participant wellbeing or interfere with the achievement of the trial's objectives. Such a decision should only be taken in consultation with the Chief Investigator. Participants will be encouraged to continue to attend trial visits for sampling and safety monitoring.

Discontinuation of dosing is essential following a grade 3 or 4 clinical or laboratory event (confirmed on examination or repeat testing respectively) which is considered possibly, probably or definitely related to the vaccine and which did not resolve within 72 hours.

Provided the participant agrees they will continue to be followed up for the duration of the study and samples will be collected at the allotted times.

Dosing must be discontinued in participants who become pregnant or HIV infected.

Participants may decide to discontinue dosing. They will be encouraged to provide a reason, and to remain in follow-up. The appropriate CRF should be completed as soon as possible if a patient chooses to stop receiving vaccines or to withdraw from the trial, and within 24 hours of a decision being taken to discontinue a participant when that decision is informed by an adverse event (**section 8.1**).

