The AEs for the randomised subjects will be coded by MRC CTU staff using MedDRA. If a participant reports the same event more than once then the worst severity and worst relationship to trial vaccine will be taken. Discrepancies between diary card and CRF reports will be queried by the monitor if unclear. It is assumed that the grade assigned by the clinician is more accurate, and this will be the grade reported in the ITT analysis tables, prepared by MRC CTU. If the diary card grade is worse, this will be foot noted.

All safety end-points will be graded by the Clinical Investigators.

Safety outcomes for the randomised participants will be reported overall with proportion and 95% confidence interval, and by group and time-point, and by relationship to study product, and method.

For the primary ITT analysis of safety endpoints (as defined in **section 10.2**), results will be expressed as a proportion with confidence interval, and groups compared using Fisher's exact test.

Safety outcomes for the non-randomised participants will be reported separately.

10.4.5

Tolerability Outcomes

The tolerability data from the questionnaires will not be part of the SAP or reported in the Clinical Study Report.

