2.3. Analysis datasets

The statistical analysis will be conducted on randomised participants on both an Intention-to-Treat (ITT) and a Per-Protocol (PP) basis. This is a phase I trial concerned with both safety and efficacy, ITT provides estimates of effectiveness in a 'real-world' setting where participants missed doses or became lost-to-follow-up, PP estimates efficacy under ideal conditions.

- Intention-To-Treat (ITT) dataset: all participants randomised and given at least one immunisation in the trial.
- Per-Protocol (PP) dataset: all participants randomised and immunised with all scheduled immunisations, completing the trial with no major protocol deviations.

A safety analysis population is also defined as all participants receiving at least one dose of trial medication.

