3.1. Primary Endpoints

3.1.1. Safety

Any of the following events occurring between week 0 and week 22 will be included in the analysis:

- Grade 3 or above local solicited adverse event (Table 2)
- Grade 3 or above systemic clinical and laboratory solicited adverse event (Table 2)
- Any grade of adverse event that results in a clinical decision to discontinue further immunisations
- Any grade of adverse event within 7 days of receiving intradermal and standard intramuscular vaccinations with or without electroporation

Table 2: Solicited adverse events

Type	Event
Local AEs (immunisation site)	Discomfort Redness Swelling (soft) Induration (hard) Blisters
Systemic Clinical AEs	Abnormally raised temperature Chills Myalgia/flu-like general muscle aches Malaise (excess fatigue) Headache Nausea Vomiting
Systemic Laboratory AEs	Abnormalities in: Creatinine, AST, ALT, alkaline phosphatase, total bilirubin, glucose, Hb, total WCC, neutrophils, lymphocytes, platelets

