4.5. Primary Analysis

4.5.1. Safety

For each arm the proportion and its 95% CI will be reported for participants with a primary safety endpoint as defined in 3.1.1. The proportion with events will be compared in a pairwise manner between the three randomised groups, using Fisher's exact tests.

Grade 3 or above safety endpoints and any endpoints that lead to discontinuation of the vaccine regimen will be described, and a full listing of all events for each participant will be filed in the statistical master file.

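### SAP 2.3 and 4.5.1 allow the primary safety proportions to be computed on a per-protocol set that drops participants whose adverse event stopped dosing

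*SAP*

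**What the plan says.** SAP 4.5.1 sets out the primary safety analysis: "For each arm the proportion and its 95% CI will be reported for participants with a primary safety endpoint as defined in 3.1.1", followed by pairwise Fisher's exact tests between the three groups. SAP 4.6.1 handles the secondary safety endpoint in the same way. Neither section names an analysis set, and the shell for Appendix Table 2 has one unlabelled N per arm.

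The general rule is in SAP 2.3: "The statistical analysis will be conducted on randomised participants on both an Intention-to-Treat (ITT) and a Per-Protocol (PP) basis". The ITT set there is everyone who was randomised and received one or more immunisations. The PP set is narrower, and the SAP words it as "all participants randomised and immunised with all scheduled immunisations, completing the trial with no major protocol deviations".

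SAP 2.3 also defines a safety population of everyone given at least one dose, but no later section uses it.

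The third item of the primary safety endpoint in SAP 3.1.1 is "Any grade of adverse event that results in a clinical decision to discontinue further immunisations". Protocol 6.1.5 adds a mandatory route: "Discontinuation of dosing is essential following a grade 3 or 4 clinical or laboratory event", where the event is confirmed, judged related to vaccine and unresolved within 72 hours.

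Protocol 10.4.4 does name a set for this analysis: "For the primary ITT analysis of safety endpoints". Protocol 10.4.2.1 reserves the per-protocol population for immunogenicity.

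**The concern.** PP membership depends on receiving all four immunisations, and one component of the primary safety endpoint is an adverse event that prevents this. A PP safety proportion is therefore computed among people selected partly for not having had the outcome. The SAP as written calls for that result, because 2.3 makes no exception for safety. SAP 4 also says that the trials unit analyses safety and tolerability while immunogenicity is analysed elsewhere. An analyst at the unit who follows 2.3 would thus be applying PP mainly to safety data.

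At stake is a second set of safety figures that looks more reassuring than the data warrant. Protocol 2.2.4 says a route will not be explored further if safety is unacceptable, judged by the proportion with a grade 3 or above solicited event or an investigator decision to stop. The discontinuations in that measure are what PP removes.

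**Working it through.** **Inputs.** Eight participants per arm (SAP 2.2), Wilson 95% intervals (SAP 4), pairwise Fisher's exact tests (SAP 4.5.1). The documents give no expected event rate or stopping rate, so every event count below is an assumption for illustration.

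**Reproducing the plan's own figures.** With z = 1.96, the Wilson interval is [p + z²/2n ± z√(p(1−p)/n + z²/4n²)] / (1 + z²/n). For 2/8:

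- centre = (0.25 + 0.240)/1.480 = 0.331
- half-width = (1.96/1.480) × √(0.0234 + 0.0150) = 0.260
- interval = 7.1% to 59.1%

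SAP Table 3 prints 7 to 59%. Its other entries for N = 8, 7, 6 and 5 also reproduce to within rounding.

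**Who leaves PP because of the outcome.**

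- An adverse event that stops dosing after dose 1, 2 or 3: always leaves, including stops required by protocol 6.1.5.
- A grade 3 event that resolves and does not stop dosing: stays.
- Any event after dose 4: does not by itself remove the participant.
- An adverse event within 7 days that does not stop dosing: stays.

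**Discontinuation item alone.** Every such stop before dose 4 leaves both numerator and denominator, so 1/8, 2/8 and 3/8 in ITT become 0/7, 0/6 and 0/5 in PP.

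**Composite of SAP Appendix Table 2** (grade 3+ solicited event or discontinuation). Let e of 8 have the event and d of those stop before dose 4, with everyone else staying in PP. ITT gives e/8; PP gives (e−d)/(8−d).

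| e | d | ITT (95% CI) | PP (95% CI) |
|---|---|---|---|
| 2 | 1 | 25.0% (7.1–59.1) | 1/7 = 14.3% (2.6–51.3) |
| 2 | 2 | 25.0% (7.1–59.1) | 0/6 = 0% (0–39.0) |
| 3 | 1 | 37.5% (13.7–69.4) | 2/7 = 28.6% (8.2–64.1) |
| 3 | 2 | 37.5% (13.7–69.4) | 1/6 = 16.7% (3.0–56.4) |
| 3 | 3 | 37.5% (13.7–69.4) | 0/5 = 0% (0–43.4) |

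In general, with event risk p and share s of event participants who stop, PP risk = p(1−s)/(1−ps). This is below p whenever p is between 0 and 1 and s is above 0. For p = 25% it is 0.1875/0.9375 = 20%, 0.125/0.875 = 14% and 0.0625/0.8125 = 8% at s = 25%, 50% and 75%.

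**Between arms.** From the same formula the PP odds are (1−s) × p/(1−p). The PP odds ratio of arm A to arm B is therefore the ITT odds ratio times (1−s_A)/(1−s_B).

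- Equal stopping shares leave the odds ratio unchanged, and only events and power are lost. Power loss shows when 5/8 v 0/8 (Fisher p = 0.026) becomes 4/7, 3/6 or 2/5 v 0/8 as one, two or three of the five stop: p = 0.026, 0.055 and 0.128.
- Unequal shares can move the comparison either way. With 2/8 v 2/8 in ITT and both event participants stopping in one arm only, PP gives 2/8 v 0/6, a difference that ITT does not show.

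**The case against.** The strongest reply is that the protocol already settles the matter. Section 10.4.4 makes the primary safety analysis ITT and refers to ITT tables from the trials unit, and section 10.4 says the SAP is to be based on that summary. SAP 2.3 explains PP in terms of efficacy, the shells contain no table labelled PP, and SAP 4.5.1 requires discontinuation and grade 3+ events to be described and all events to be listed. This largely stands. The main result is protected if the protocol is followed, and no event disappears from the record. It does not remove the instruction in SAP 2.3 or supply the set missing from 4.5.1 and 4.6.1.

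A reader might infer four stronger things that the documents do not support.

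- *That PP Fisher tests are biased towards no difference.* This is not general, as the odds-ratio result shows.
- *That the full four-item endpoint of SAP 3.1.1 is distorted to the same degree.* Its fourth item is any adverse event within 7 days. Protocol 2.2.2.3 reports transient pain in virtually all recipients of the intramuscular device, so that proportion may be near 100% in either set. The figures above apply to the discontinuation item and the Appendix Table 2 composite only.
- *That the N = 7, 6 and 5 columns of SAP Table 3 show PP safety tables are intended.* The table also serves vaccine responses, where smaller denominators are natural.
- *That a route would be kept or dropped on PP figures.* Protocol 2.2.4 names no set and no threshold.

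The illustrative counts may also prove high. Protocol 2.2.5 reports that all volunteers completed immunisations in the first trial of electroporation with an HIV DNA vaccine, and that one participant chose to stop because of pain in the sister study. With no stops before dose 4, this mechanism has no effect.

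**Conclusion.** The point holds as a fault in the SAP's rule for analysis sets. As written, the SAP calls for a PP version of the safety analysis, and that version excludes participants because they had the outcome. The PP discontinuation proportion is zero by construction for stops before dose 4; that follows from the definitions alone. The downward bias in the Appendix Table 2 composite depends on how many event participants stop, and on the simplification that participants without an event remain in PP. Under the assumed counts, one to three stops in an arm of eight lower the proportion by about 9 to 38 percentage points (37.5% to 28.6% at the least, 37.5% to 0% at the most). The intervals are wide and overlap throughout.

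The direction of any effect on between-arm comparisons is not fixed. Nor do the documents support saying that the trial's main safety result is biased, since protocol 10.4.4 places it on ITT. The point is worth correcting before the analysis is run, because the SAP departs from the protocol here and the PP safety figure has no sound interpretation.

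**What to change.** In SAP 4.5.1 and 4.6.1, state that safety proportions, intervals and Fisher tests use all randomised participants given at least one immunisation, that is, the ITT set as already defined. In SAP 2.3, limit the PP set to immunogenicity, which restores the split in protocol 10.4.2.1 and 10.4.4.

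ITT is a better choice here than the SAP's safety population. That population is not restricted to randomised participants, so it could admit the non-randomised replacements described in protocol 10.4.1. Those should be reported separately, as protocol 10.4.4 provides. The SAP should either give the safety population that use or remove it.

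The cost is a few sentences and a set label on the table shells. No new data are needed, nothing changes for participants, and there are fewer tables to produce.

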To date, the 20 clinical trials that have been completed or are currently ongoing have enrolled over 600 subjects in the electroporation arms of the studies (including subjects receiving either the DNA vaccine candidate or placebo). The device has been used for administration of DNA injections of up to 1.0 ml volume and 4.0 mg DNA dose per injection site. Subjects have received the vaccine candidate either as a single injection in one muscle site (total DNA dose up to 4.0 mg per administration time point) or as 2 injections in 2 separate muscle sites (total DNA dose up to 8.0 mg per administration time point). Subjects given the DNA dose as a single injection have received up to 5 TDS-IM injections and up to 4.0 mg DNA, and subjects administered with the DNA dose in 2 injections received up to 10 administrations (i.e., 20 total TDS-IM injections).

Acute adverse responses associated with the use of the device include transient pain associated with electroporation-induced localised muscle contractions reported by virtually all subjects. This has occasionally been accompanied by mild paresthesia in the administered limb lasting for several seconds to minutes after application of electroporation. Mild, transient bleeding at the sites of electrode/needle penetration is commonly observed following removal of the device from the administration site. Local site reactogenicity, including injection site soreness, erythema, and/or induration of mild to moderate severity, has been commonly reported following electroporation-mediated DNA delivery. Mild to moderate bruising at the administration site has been observed occasionally. The local site reactions typically resolve within 24-72 hours following administration, but, in rare instances, local site soreness has been reported to persist for up to one week.

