All volunteers will receive 3 immunisations of 2.0mg DNA IM and 0.6mg DNA ID and the immunisations will be administered with or without EP as described in table 1. In a supportive rabbit GLP toxicity study which was carried out with the same vaccine, the individual IM dose was 2mg, this was given for up to six administrations was shown to be well tolerated in rabbits (CR 525569) and lack of DNA persistence or distribution beyond the site of administration was demonstrated in rats (CR525574). Furthermore, a previous Phase I trial to use electroporation (EP) for the delivery of a DNA vaccine for HIV demonstrated increased immunogenicity in the absence of associated safety concerns [44] [62].

CN54gp140 Doses

We will give 1 immunisation of 50 μ g CN54gp140. In MucoVac 2 there was no significant impact on the magnitude of the responses after reducing the dose from 100 μ g to 20 μ g although this was in the presence of adjuvant.

2.2.4

Possible Next Steps

The following hypotheses will be explored with a view to informing the design of future trials both in terms of size and selection of methods:

- That each of the methods and combination regimens delivered with and without EP will be safe and acceptable
 - If any of the methods or regimens have unacceptable safety defined in terms of the proportion of participants that experience a grade 3 or above solicited adverse event or an event that leads to an investigator decision to discontinue immunisations, then there will be no further exploration of the route with the product/regimen.
- That immunisation via the combined IM+ID methods will elicit balanced immune responses.
- That EP will augment antibody responses to both ID and IM.

- That the greatest proportion of individuals will respond and make significantly greater antibody responses in group 3 (ID/EP + IM/EP) relative to the other groups. If EP is shown to impact upon the proportion of individuals making systemic IgG without compromising safety/tolerability, the strategy would be taken forward into future trials.

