2.1. Randomisation

Participants will be block-randomised using a computer-generated algorithm with a back-up manual procedure and randomisation will be stratified on the basis of gender. The randomisation lists are generated and checked by the trial statistician, and stored securely in the trial database.

Participants are randomised 1:1:1 to ID/EP, IM/EP or ID/IM/EP. Randomisation is unblinded.

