2.2. Sample Size

It is not the remit of this Phase I trial to recruit a sufficient number of participants to be statistically confident about the differences between groups. By the end of this study 8 participants will have been randomised to each method of delivery.

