3.2. Secondary Endpoint

3.2.1. Safety

Any grade of adverse event, local to the ID and IM injection sites that start within 7 days after Doses 1-3.

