3.3.2. Tolerability

- Pain scores at 0, 10 and 30 minutes following vaccination with EP

4. Statistical Analyses

Analyses of safety and tolerability endpoints for randomized participants will be performed at the MRC CTU at UCL. Immunogenicity data are not held at the CTU, and will be analysed elsewhere.

Adverse events and vaccine responses will be described as frequencies with 95% confidence intervals. Confidence intervals will be calculated using Wilson intervals, suitable for small sample sizes (table 3).

Table 3. Wilson intervals

Number of events	N=8		N=7		N=6		N=5	
	%	95% CI						
0	0%	0,32%	0%	0,35%	0%	0,39%	0%	0,43%
1	13%	2,47%	14%	3,51%	17%	3,56%	20%	4,62%
2	25%	7,59%	29%	8,64%	33%	10,70%	40%	12,77%
3	38%	14,69%	43%	16,75%	50%	19,81%	60%	23,88%
4	50%	22,78%	57%	25,84%	67%	30,90%	80%	38,96%
5	63%	31,86%	71%	36,92%	83%	44,97%	100%	57,100%
6	75%	41,93%	86%	49,97%	100%	61,100%		
7	87%	53,98%	100%	65,100%				
8	100%	68,100%						

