4.6. Secondary Analysis

4.6.1. Safety

For each arm the proportion and its 95% CI will be reported for participants with a secondary safety endpoint as defined in 3.2.1. CIs and significance tests will be reported similarly to the primary safety endpoint.

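### The any-grade safety endpoints are formally compared only by yes/no Fisher tests that are probably near their ceiling, and no between-arm difference with an interval is planned

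*SAP*

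**What the plan says.** SAP 4.5.1 reports, for each arm, the proportion of participants with a primary safety endpoint and its 95% CI, and then: "The proportion with events will be compared in a pairwise manner between the three randomised groups, using Fisher's exact tests". For the secondary endpoint, SAP 4.6.1 adds: "CIs and significance tests will be reported similarly to the primary safety endpoint". Protocol 10.4.4 also names Fisher's test for the primary safety analysis.

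The primary set in SAP 3.1.1 has four items: grade 3+ local solicited events, grade 3+ systemic solicited events, events leading to discontinuation, and (item 4) any-grade events within 7 days of vaccination. The secondary endpoint in SAP 3.2.1 is "Any grade of adverse event, local to the ID and IM injection sites that start within 7 days after Doses 1-3".

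On size, SAP 2.2 states: "By the end of this study 8 participants will have been randomised to each method of delivery". SAP 2.2 and Protocol 2.2.1 and 10.3 all say that the trial is not sized for comparisons between groups.

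**The concern.** The secondary objective (SAP 1.2) is comparative: safety of the electroporation devices against standard injection. For the primary and secondary safety endpoints, the formal comparison between arms is a p-value on a yes/no proportion, with no estimate of how far apart the arms are.

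For the two any-grade endpoints, the yes/no outcome may hardly vary. All three groups in SAP Table 1 receive electroporation at one or both sites at each DNA dose. Protocol 2.2.2.3 reports, for the intramuscular device, "transient pain associated with electroporation-induced localised muscle contractions reported by virtually all subjects". For the intradermal device it describes pinpoint eschar and transient local reactions as common. If nearly everyone has at least one mild event, the arms can differ in severity while the yes/no proportions stay the same.

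SAP 4.5.1 refers to a participant with an endpoint as defined in 3.1.1. If that means any of the four items, item 4 would carry the ceiling into the primary test as well. The title of shell Table 2 leaves item 4 out, so the two places do not agree.

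**Working it through.** **Inputs**
- Arm size: 8 (SAP 2.2). Allocation: "Participants are randomised 1:1:1 to ID/EP, IM/EP or ID/IM/EP" (SAP 2.1).
- Alpha and sidedness: not stated for the Fisher tests. I assume two-sided 0.05, in line with the opening of SAP section 4: "Adverse events and vaccine responses will be described as frequencies with 95% confidence intervals".
- Event rates per arm and grade distributions: none given. All rates below are assumptions.

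**1. The plan's own figures.** The Wilson limits are [p + z²/2n ± z√(p(1−p)/n + z²/4n²)] / (1 + z²/n), with z = 1.96 and n = 8.
- 0/8 gives 0 to 32.4%, 4/8 gives 21.5 to 78.5%, and 8/8 gives 67.6 to 100%.
- SAP Table 3 prints 0–32, 22–78 and 68–100. All its other cells also reproduce to the rounded percent.

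**2. Fisher thresholds, 8 v 8**
- 0 v 5: p = 2 × C(8,5)/C(16,5) = 2 × 56/4368 = 0.026.
- 0 v 4: p = 2 × C(8,4)/C(16,4) = 2 × 70/1820 = 0.077.

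| Events in lower arm | Fewest in other arm for p<0.05 | p | p with one fewer |
|---|---|---|---|
| 0 | 5 | 0.026 | 0.077 |
| 1 | 6 | 0.041 | 0.119 |
| 2 | 7 | 0.041 | 0.132 |
| 3 | 8 | 0.026 | 0.119 |
| 4 or more | none | – | – |

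Summing over all outcomes, the true size of each test is at most 2.1% (reached when both rates are 50%).

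**3. Near the ceiling**
- 8 v 8 and 7 v 8 both give p = 1.00.
- 6 v 8 gives p = 2 × C(8,2)/C(16,2) = 2 × 28/120 = 0.47.
- If one arm is certain to show 8/8, the test rejects only when the other shows 3 or fewer. For a true 90% that probability is 0.04%; for 80% it is 1.0%.

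**4. How close the ceiling may be.** If a local reaction follows a fraction q of DNA doses, independently across doses, the chance of at least one in three doses is 1 − (1 − q)³. For q = 60% this is 93.6%; for q = 90% it is 99.9%. Both q and independence are assumptions. If reactions cluster in the same people, the cumulative rate is lower.

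**5. What a difference with an interval would show.** With arm proportions p₁, p₂ and Wilson limits (l₁, u₁), (l₂, u₂), the Newcombe limits are d − √((p₁−l₁)² + (u₂−p₂)²) and d + √((u₁−p₁)² + (p₂−l₂)²).
- 4/8 v 0/8: d = 50 points; lower 0.50 − √(0.285² + 0.324²) = 0.068; upper 0.50 + 0.285 = 0.785.
- 0/8 v 0/8: d = 0, limits ±32.4 points.

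**6. Comparing severity instead.** Exact rank-sum test on maximum grade, 8 v 8, 1,500 simulations per row. The grade distributions are assumed.

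| Grades 0/1/2/3, arm A (%) | Arm B (%) | Rank test power | Any-grade Fisher |
|---|---|---|---|
| 5/75/15/5 | 5/45/40/10 | about 13% | 0% |
| 5/75/15/5 | 2/28/55/15 | about 40% | 0% |
| 5/80/12/3 | 0/20/55/25 | about 74% | 0% |

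In the middle row, grade 2+ rises from 20% to 70%.

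**The case against.** The strongest reply is that much of what is wanted is already planned. SAP 4.5.1 gives per-arm intervals, describes grade 3+ and discontinuation events, and lists every event. Shell Tables 2 to 7 show grade, count, dose number, relationship and duration. SAP 4.7 would apply Welch tests to continuous exploratory outcomes, which include pain scores, although Protocol 10.4.5 keeps tolerability out of the SAP. A reader might infer that a Fisher p-value is the only between-arm safety output. That is not so. What is missing is a formal comparison of severity, and a difference with an interval.

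A reader might also infer that a non-significant test would clear electroporation for later trials, because Protocol 2.2.4 sets the condition "without compromising safety/tolerability". The documents do not support this. The same section defines unacceptable safety by the proportion with a grade 3+ solicited event or an event leading to discontinuation. No passage equates a non-significant test with equal safety.

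Nor can it be said that a real difference would simply be missed. A true 0% v 70% has 81% power, and the ceiling does not reach grade 3+ events. Low power is disclosed in both documents and is not an error.

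The ceiling itself is a judgement. The near-universal pain refers to the intramuscular device, which Group 1 does not receive, and no rate is given for the intradermal device.

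What stands is that the any-grade tests are probably uninformative and that the size of any difference goes unreported.

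**Conclusion.** The point holds in a limited form. For the primary and secondary safety endpoints, the formal between-arm comparison is yes/no only and carries no interval for the difference. For SAP 3.1.1 item 4 and SAP 3.2.1 it is probably close to uninformative: 6 v 8 gives p = 0.47, and once the lower arm has 4 events no result can reach 0.05.

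This rests on two-sided 5%, on 8 analysed per arm, and on any-grade reactions being as common as the device history suggests. If any-grade rates turn out moderate, the ceiling argument weakens, but the case for reporting differences with intervals remains.

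**What to change.** 1. In SAP 4.5.1 and 4.6.1, report each pairwise difference in proportions with a Newcombe 95% CI as the main between-arm result. It is built from the Wilson limits that the SAP already uses. Keep Fisher's test, as Protocol 10.4.4 requires.
2. Analyse 3.1.1 item 4 separately from the grade 3+ and discontinuation components, and bring 3.1.1 and shell Table 2 into line.
3. For 3.1.1 item 4 and 3.2.1, compare maximum grade per participant between arms by an exact Wilcoxon test. Present the any-grade proportion as description. The Fisher p-value that Protocol 10.4.4 calls for on item 4 can be printed beside it.
4. State in the SAP that a non-significant test is not evidence of equal safety.

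The cost is SAP wording and a small extra analysis on data already collected. There are two drawbacks. The Newcombe interval can exclude zero when Fisher's p exceeds 0.05 (0 v 4: about 7 to 78 points, p = 0.077), so it should be read as estimation and not as a second test. The rank test is also weak at this size, with about 40% power even for the assumed rise in grade 2+ from 20% to 70%.

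Replacing Fisher with a less conservative exact test is not proposed. It would depart from Protocol 10.4.4 and would not cure the ceiling: Boschloo's test has about 0.5% power for 90% v 99%.
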